### 3.2 Overall Study Design and Plan

The study is planned to start in Q3 2021 and to be clinically completed by Q4 2024. The study will be a prospective, multicenter, randomized, double-blind, parallel group, placebo-controlled, Phase III superiority study in a minimum of █ pediatric patients with confirmed diagnosis of moderate to severe PANS with prominent and stable OCD symptoms (i.e. CGI—Severity-OCD rating of  $\geq 4$  or higher on 2 ratings without a change of more than 1 unit between measurements). The study includes an additional double-blind, crossover safety and efficacy follow-up phase of three infusions of Panzyga or placebo administered over 2 days every three weeks for a total of nine weeks.

[figure not shown]
After the first █ patients had been enrolled, the study enrollment was put on hold to further enhance the safety monitoring of Panzyga administration. The study resumed only after the Independent Data Monitoring Committee (IDMC) had reviewed unblinded safety and PK data of these █ patients and given the green light to pursue the study.

Up to 30 sites are projected to participate in this clinical study.

Eligible patients will be randomized 1:1 to two possible treatment sequences:

- (Panzyga – Placebo): three administration cycles with Panzyga, followed by three administration cycles with placebo
- (Placebo – Panzyga): three administration cycles with placebo, followed by three administration cycles with Panzyga

Patients will undergo repeated efficacy and safety assessments relating to each cycle. After completion of the first double-blind treatment period, blinded crossover assignment will be done; patients previously in the Panzyga arm will be assigned placebo and patients previously in the placebo arm will be assigned Panzyga, administered at the same regimen. Figure 1 depicts the study design. Rescreening is allowed for patients who were eligible based on the onset of symptoms, but have recently initiated CBT, psychotropic medication, corticosteroids, anti-virals, or antibiotics, provided these treatments are completed within the timelines stated in the exclusion criteria (Section 4.1.2).

**Figure 1: Scheme of Study Design**

### 3.3 Discussion of Study Design and Choice of Control Group(s)

#### 3.3.1 Study Design

Octapharma designed this prospective, multicenter, randomized double-blind superiority study comparing Panzyga with placebo (0.9% w/v sodium chloride) to confirm efficacy and safety of Panzyga in PANS patients. The study includes an additional double-blind, crossover safety and efficacy follow-up phase. In case of clinically important deterioration during the study, patients will be discontinued from the study, have termination visit procedures performed, and may optionally receive standard of care treatment at the site according to the treating physician.

Due to the previously described uncertainty on the expected effect size, the study will be set up in an adaptive, two-stage design using enrichment. This involves an interim analysis by an independent statistician after █ patients have completed the nine week treatment period (the entire study team will remain blinded until the end of the study).

In the context of this interim analysis, effect sizes for different subpopulations will be studied and statistically compared between treatments. After the interim analysis, the study may be adapted with respect to the study cohort and sample size. This may involve the exclusion of defined subgroups of patients for which no substantial treatment effect could be established.

Based on the observed effect sizes in the interim analysis, a re-estimation of the sample size for the post-interim analysis study part will be performed and the protocol may be amended accordingly. More details are provided in Section 9 of this protocol.

The study population will be prospectively balanced according to the choice of antibiotic prophylactic treatment, disease type (PANS/PANDAS) and treatment with stable dose of SSRIs.

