During the first phase of the study (i.e. three infusion cycles), patients will repeat the behavioral and laboratory parameter assessments performed at Baseline and the primary endpoint will be evaluated at Week 9 Visit. Data for evaluation of secondary endpoints will also be collected. Thereafter, crossover treatment assignment will occur in a blinded fashion for the second phase of the study. In the second phase of the study (Week 9, 12, 15, and 18 visits), patients who received Panzyga in the first phase will be assigned placebo and vice versa. During this second phase, three infusion cycles of either Panzyga (1 g/kg BW daily for two consecutive days) or placebo (0.9% w/v sodium chloride infusion equivalent in volume to 1 g/kg BW Panzyga daily for two consecutive days) will be given at three-week intervals at the study site. The patients' conditions will be monitored throughout the infusion session. Upon completion of the second phase of the study, at the Week 18 Visit, data for evaluation of secondary endpoints, including durability of the clinical benefit and safety data, will be collected.

If a patient shows worsening of their symptoms based on CGI-Improvement ratings they will be presented to the site PI for review and treatment planning. Patients for whom worsening continues at a minimal level ("5" or "mildly worse") for an extended period of six weeks (2 visits) or moderately or greater level ("6" or "7"; much worse or very much worse) since last visit (up to three weeks) will be considered for premature withdrawal from the study drug and administration of appropriate standard of care treatment unless clinical interventions using approved study procedures and/or medications have a reasonable likelihood to improve symptoms. Patients who experience an emergency worsening of symptoms may at the discretion of the site clinician be withdrawn from the study drug at any time to obtain necessary standard of care treatment. In addition, patients who develop exclusionary criteria (e.g. bipolar disorder, suicide attempt) will be withdrawn from the study drug and will receive appropriate standard of care treatment. All patients withdrawn from the study drug prematurely will be asked to continue the study as planned with modification of the study schedule (e.g. IMP administration and related to it safety lab tests will be omitted). Details of concomitant medications and procedures administrated per standard of care will be captured in patient case reports.

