Patients who need to be discontinued from the study will undergo a termination visit and will be treated according to standard of care at the site according to the treating physician.

The study assessments and scheduled time points for the first and second phases of the crossover study are summarized in the flow charts following this Study Outline and in Section 15.2 for sites in Europe.

Name of Sponsor/Company: Octapharma Pharmazeutika Produktionsges.m.b.H.	
Name of Investigational Product: Panzyga	Protocol Identification Code: NGAM-13
Name of Active Ingredient: Immune Globulin Intravenous, Human 10%	Date of Final Protocol: 21 July 2023

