## 4.3 Withdrawal and Replacement of Patients

### 4.3.1 Premature Patient Withdrawal from the Study

Patients have the right to withdraw from the study at any time for any reason, without the need to justify their decision. The investigator also has the right to withdraw patients in case of AEs, poor compliance, or other reasons. Since an excessive rate of withdrawals can render the study non-interpretable, any unnecessary withdrawal of patients should be avoided.

For any withdrawals after study entry, the investigator will obtain all the required details and document the reason(s) for discontinuation in the eCRF. If the reason for withdrawal of a patient is an AE, the main specific event or laboratory test will be recorded in the eCRF, and the investigator will make thorough efforts to clearly document the outcome.

Patients who terminate the study prematurely are considered drop-outs. The investigator will schedule an Early Termination Visit, which is identical to the Week 18 Visit procedures.

Other reasons for premature termination of patients may be:

- Withdrawal of patient's consent.
- Pregnant and lactating patients will be immediately excluded from the study.
- Investigator's opinion that the patient may be severely harmed if he/she continues study participation, namely by the treatment and procedures requested by the study protocol.
- Patients do not comply with the study protocol.

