### 4.3.2 Premature Patient Withdrawal from Study Treatment

Patients may be withdrawn from study treatment for the following reasons:

- Occurrence of a condition or disease that interferes with the study treatment or represents an exclusion criterion.
- Administration of IVIG other than Panzyga. All patients who received at least one dose of the study treatment should be followed up per protocol until the study end without administration of the study product.

- Occurrence of an AE or SAE, which in the opinion of the investigator, precludes further treatment with study medication (Section 7.3.2).

If a patient shows worsening of their symptoms based on CGI-Improvement ratings, they will be presented to the site PI for review and treatment planning. Patients for whom worsening continues at a minimal level ("5" or "mildly worse") for an extended period of six weeks (2 visits) or moderately or greater level ("6" or "7"; much worse or very much worse) since last visit (up to three weeks) will be considered for premature withdrawal from the study drug and administration of appropriate standard of care treatment unless clinical interventions using approved study procedures and/or mediations have a reasonable likelihood to improve symptoms. Patients who experience an emergency worsening of symptoms may at the discretion of the site clinician be withdrawn from the study drug at any time to obtain necessary standard of care treatment. In addition, patients who develop exclusionary criteria (e.g. bipolar disorder, suicide attempt) will be withdrawn from the study drug and will receive appropriate standard of care treatment. All patients withdrawn from the study drug prematurely will be asked to continue the study as planned with modification of the study schedule (e.g. IMP administration and related to it safety lab tests will be omitted). Details of concomitant medications and procedures administrated per standard of care will be captured in patient case reports.

The eCRF will contain an End of Treatment and an End of Study page. The End of Treatment page will record whether the patient will be followed up per protocol, to allow for correct patient status tracking and to provide the reason for the drug withdrawal.

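### Protocol 3.3.1 takes deteriorating patients out of the study, while 4.3.2 and the Study Outline stop only study drug; a site following 3.3.1 before Week 9 loses the primary CY-BOCS score for an outcome-related reason

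*Protocol*

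**What the plan says.** **Rule A: leave the study.** Protocol 3.3.1, in the discussion of study design: "In case of clinically important deterioration during the study, patients will be discontinued from the study, have termination visit procedures performed". It sets no threshold, and standard of care afterwards is optional.

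**Rule B: stop study drug, stay in the study.** Under Protocol 4.3.2, patients with six weeks of mild worsening, or with a CGI-I rating of 6 or 7 since the last visit, "will be considered for premature withdrawal from the study drug and administration of appropriate standard of care treatment", unless permitted interventions are reasonably likely to help. For acute cases: "Patients who experience an emergency worsening of symptoms may at the discretion of the site clinician be withdrawn from the study drug". Patients who develop an exclusion condition, such as a suicide attempt, also come off study drug. For all of these, 4.3.2 and the Study Outline (Study Procedures) say the same thing: "All patients withdrawn from the study drug prematurely will be asked to continue the study as planned with modification of the study schedule". Section 4.3.2 also states "All patients who received at least one dose of the study treatment should be followed up per protocol until the study end". That sentence sits under the bullet on other IVIG products but is worded for every dosed patient.

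**Leaving the study in general.** The Study Outline adds "Patients who need to be discontinued from the study will undergo a termination visit" without saying who those patients are. Section 4.3.1 lets the investigator withdraw a patient for adverse events, poor compliance or other reasons, or where continued participation may cause severe harm. It also warns: "Since an excessive rate of withdrawals can render the study non-interpretable, any unnecessary withdrawal of patients should be avoided". For patients who leave: "The investigator will schedule an Early Termination Visit, which is identical to the Week 18 Visit procedures".

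**Analysis.** The primary endpoint is the change in total CY-BOCS from Baseline to Week 9. SAP 8.2 keeps every randomized patient in the primary analysis. SAP 8.3 imputes a missing Week 9 score by multiple imputation under missing at random, with a sensitivity analysis that fills in the placebo median change. Under SAP 4.1, dropout after Week 9 does not count against the primary objective.

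**The concern.** The same event, a child getting worse, leads to study exit under one section and to continued follow-up under another. If a site applies 3.3.1 before Week 9, a primary outcome value that 4.3.2 would have kept is missing, and it is missing because of the outcome. An exit CY-BOCS is probably taken, since SAP 4.1 schedules one at Week 18 or the final visit. No readable text lets that exit score stand as the Week 9 value.

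What is at stake is the number of observed primary values and, depending on the imputation model and on what standard of care does for these children, the estimated treatment difference.

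**Working it through.** **1. Do the two rules meet?** One could read 4.3.2 as covering moderate worsening and 3.3.1 as covering severe worsening. But 4.3.2 already includes the top CGI-I categories, emergency worsening and suicide attempt, and it keeps all of them in the study off drug. That leaves no evident class of more severe deterioration for 3.3.1 to govern. The exit routes in the Study Outline and in 4.3.1 do not name deterioration as such.

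**2. Inputs for an illustration.** The planned sample size, SD and effect are blacked out, so every value here is an assumption except the 10% dropout allowance (Study Outline, Number of Patients), which is used only as a yardstick.
- SD of CY-BOCS change: 6, 7 and 8 at Weeks 3, 6 and 9. Adjacent-visit correlation 0.7, squared between Weeks 3 and 9.
- Mean Week 9 change: -8 on Panzyga and -4 on placebo, linear over visits.
- Exit after Week 6 if the Week 6 change plus noise (SD 3.5) exceeds one cutoff common to both arms, set to give 7.5% exits overall. This results in 5.1% on Panzyga and 9.9% on placebo.
- r: average improvement in the Week 9 score, from standard of care, among these patients had they been retained. Taken as 0, 4 or 8 points.

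**3. Formula.** Differences are Panzyga minus placebo, so negative values favor Panzyga. Let D_full be the difference with no exits and no rescue, D_est the estimate after exits, and e_P and e_0 the exit fractions on Panzyga and placebo.

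Difference that 4.3.2 would collect: D_ret = D_full + r × (e_0 − e_P)

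Shift = D_est − D_ret = (D_est − D_full) − r × (e_0 − e_P)

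**4. Numbers.** e_0 − e_P = 0.099 − 0.051 = 0.048, so r × 0.048 is 0, 0.192 or 0.384.
- Imputation ignoring on-study scores (simulation, 1,000,000 patients per arm): D_full = -3.98 and D_est = -3.57, so D_est − D_full = +0.41.
- Imputation by arm on Week 3 and Week 6 scores: D_est − D_full = 0.00.

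| Rescue benefit r | Imputation ignores on-study scores | Imputation uses Week 3 and Week 6 scores |
|---|---|---|
| 0 points | +0.41 | 0.00 |
| 4 points | 0.41 − 0.19 = +0.22 | 0.00 − 0.19 = -0.19 |
| 8 points | 0.41 − 0.38 = +0.03 | 0.00 − 0.38 = -0.38 |

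A positive shift makes the drug look weaker than the retained data would; a negative shift makes it look stronger. Direct simulation of the 4-point cell gives 0.22 to 0.23.

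**5. Range.** With r = 0 and imputation ignoring on-study scores:
- exits of 2.5% to 10% overall give +0.20 to +0.49;
- correlation 0.5 to 0.8 gives +0.29 to +0.47;
- a true difference of -2 gives +0.21;
- no true difference gives zero, because exits are then equal in the two arms.

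Even in this column the sign is not secure: at correlation 0.5 with an 8-point rescue it is 0.29 − 0.38 = -0.09.

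**The case against.** **The trigger in 3.3.1 is undefined, so it cannot be shown to pick out the same children as 4.3.2.** It sits in a discussion section and may be a loose summary of the Study Outline's sentence on patients who must leave. This stands in part: a tiered reading is possible, and the visit instructions in Section 6.1 and the flow charts are blacked out. But 3.3.1 is worded as mandatory, both sentences are readable, and a site has no stated way to choose between them.

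**Worsening can already lead to study exit under 4.3.1.** Under 7.3.2.2, worsening beyond the expected fluctuation that also needs treatment is an adverse event, and 4.3.1 allows withdrawal for adverse events and for other reasons. This stands. Aligning 3.3.1 therefore removes one cause of lost Week 9 scores, not all of them.

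**A reader might infer that the conflict makes the trial understate the drug effect.** It is plausible that more placebo than Panzyga patients would cross a common threshold. But patients retained under 4.3.2 receive standard of care, so their Week 9 score would be a post-rescue score. Once that is allowed for, the shift can be positive, close to zero or negative.

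**A reader might equally infer that imputation on earlier scores makes the problem vanish.** That holds only if rescue has no effect. The SAP version history records that covariates were added to the imputation, but the list is not readable, nor is the section that would define the target estimand. Neither inference is supported by the documents.

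**Exits of 7.5% are a heavy assumption.** They would use three quarters of the all-cause 10% dropout allowance. This is fair, and it is why the lower rate is shown.

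**Conclusion.** The point holds as a minor internal conflict in a rule that governs collection of the primary endpoint. The textual conflict is certain. Its consequence is conditional: a site must act on 3.3.1, and must do so before Week 9.

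On the assumed base case the shift against the data that 4.3.2 would collect runs from +0.41 to -0.38 CY-BOCS points on a true difference of -4, about a tenth of the effect either way. Where in that range it falls depends on the imputation model and on the benefit of standard of care, and the readable text settles neither. With no true treatment effect and no rescue effect the shift is zero, so on these assumptions the conflict creates no false-positive risk. The case for acting does not depend on direction: an observed Week 9 score is better than an imputed one, and 4.3.2 already intends to collect it.

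**What to change.** Reword the sentence in Protocol 3.3.1, for example:

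> In case of clinically important deterioration, patients will be managed per Section 4.3.2: study drug may be stopped, standard of care given, and the patient asked to continue scheduled visits, including the Week 9 CY-BOCS (by video conference if needed). Deterioration alone is not a reason for study discontinuation; withdrawal from the study follows Section 4.3.1.

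Video interviews are already permitted in Section 3.3.3.

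**Cost.** One short wording change, which can wait for the next amendment and follows the route in Section 10.4, with notice to up to 30 sites. A few visits that are already scheduled are retained. No new assessment or analysis is needed.

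**Limit.** Exits under 4.3.1 for adverse events or other reasons remain possible. Seeking a Week 9 score from patients who have already left would be new follow-up with its own burden, and is not proposed here.

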### 3.3.2 Control Group(s)

The study compares Panzyga with placebo and includes a double-blind, crossover phase. There is no appropriate alternative treatment available known to be effective over a nine week period that would allow for a comparative efficacy trial (and negate the need for placebo). In this study, all eligible patients diagnosed with moderate/severe PANS will receive both Panzyga and placebo, owing to the crossover design.

### 3.3.3 Study Parameters

The selected study parameters are appropriate to verify the clinical efficacy of Panzyga in PANS. With the exception of MINI-KID, all scales will be completed electronically, and sites are requested to use electronic questionnaires to reduce variability across patients and to ensure critical consistency of measurements. All assessments except CY-BOCS can be carried out by the treating physician, to prevent unblinding. A strategic central reader system has been established that serves as an independent expert panel to standardize reliability on the study's primary outcome measure (CY-BOCS). Standardization will also include a training program to ensure that all raters from different sites are reliable and remain so throughout the trial. To overcome rater variability as far as possible, the CY-BOCS rater should remain the same person. For the clinical interview scales CY-BOCS, CGI-S/I, and MINI-KID, the rater should meet the following credentials: MD/DO with Board Certification or Board Eligible in Child/Adolescent Psychiatry or related discipline; MD/DO with Board Certification or Board Eligible in Neurology/ Immunology/ Neuroimmunology; or PhD/PsyD with a degree in clinical psychology or related discipline. The clinical raters should also have significant clinical experience with psychiatric interviews and working with children with PANS. Whenever possible, raters should remain the same throughout the study for individual subjects.

The **CY-BOCS** scale score is a clinician-rated, semi-structured interview for rating the presence or absence, as well as the severity of obsessive-compulsive symptoms. Considerable data support the reliability and validity of both the adult [42, 43] and child versions of this scale [44]. The CY-BOCS yields a total obsession score, a total compulsion score and combined total score (maximum total CY-BOCS score=40). If in-person administration is not possible, the interview may be carried out via video conference (Zoom, WebEx etc.), but telephone administration without video is not permitted.

The **CGI** rating scales are commonly used measures of symptom severity, treatment response and the efficacy of treatments in clinical trials of patients with mental disorders. The Clinical Global Impression - Severity scale (CGI-S) is a 7-point scale that requires the clinician to rate the severity of the patient's illness at the time of assessment, relative to the clinician's past experience with patients who have the same diagnosis. Considering total clinical experience,

a patient is assessed on severity of mental illness at the time of rating 1 = normal; not at all ill; 2, borderline mentally ill; 3, mildly ill; 4, moderately ill; 5, markedly ill; 6, severely ill; or 7, extremely ill. The Clinical Global Impression - Improvement scale (CGI-I) is a 7-point scale that requires the clinician to assess how much the patient's illness has improved or worsened relative to a baseline state at the beginning of the intervention and is rated as: 1, very much improved; 2, much improved; 3, minimally improved; 4, no change; 5, minimally worse; 6, much worse; or 7, very much worse [45]. Telemedicine platforms such as video/phone can be utilized.

A specific and commonly used measure of OCD-related impairment is the COIS-R [46], which is a revision of the original **COIS** and is available in parallel parent- and child-report versions, assessing impairment due to OCD across multiple functional domains [47]. The Child Obsessive-Compulsive Impact Scale-Revised consists of parallel 33-item parent and child-report versions assessing impairment due to OCD across multiple functional domains (parent-report: Daily Living Skills, Family, Social, School; child-report: School, Social, Activities). Items are rated on a 4-point scale from 0 (not at all) to 3 (very much) [46]. The parent and child versions of the COIS-R exhibit good to excellent internal consistency and acceptable to good test-retest reliability across subscales [48]. The parent-report version has demonstrated sensitivity as a predictor of treatment response, while the child-report version is sensitive to treatment response for both cognitive behavioral therapy (CBT) and medication [48]. Telemedicine platforms such as video/phone can be utilized.

The Parent Tic Questionnaire (**PTQ**) is a commonly used tool suggested by Tourette syndrome international guidelines [49]. The PTQ assesses tic severity in the past week, allowing for individual parent ratings of tic presence or absence for 14 vocal tics and 14 motor tics. Additionally, the measure allows for separate ratings of tic frequency and intensity, completed for each tic. Frequency ratings range from 1 to 4 with the following anchors: weekly, daily, constantly, hourly. Intensity ratings range from 1 to 4, with higher scores indicative of greater tic intensity. The frequency and intensity ratings can be summed to yield a severity score ranging from 0 (i.e., tic is absent, thus no frequency or intensity ratings are given) to 8 for each tic. The PTQ includes subtotals for motor and vocal tic severity, which are summed to produce a total tic score. A 55% reduction and 10-point decrease in PTQ Total score were reported as optimal for defining positive treatment response. The PTQ demonstrates good internal consistency, excellent test-retest reliability, and good convergent validity with the Yale Global Tic Severity Scale (YGTSS) [50]. Completion via video conference is allowed.

The Swanson, Nolan, And Pelham Scale – Version IV (**SNAP-IV**) is a 26-item, parent- or teacher-reported scale which elicits reporting on each of the DSM cardinal symptoms of Attention-Deficit Hyperactivity Disorder (ADHD), Oppositional Defiant Disorder (ODD), and Conduct Disorder (CD) in children and adolescents. The 26-item scale also includes items on aggression, mood, and school performance and behavior. It is used extensively in ADHD and disruptive behavior disorder intervention trials and is sensitive to change [51]. Telemedicine platforms such as video/phone can be utilized.

The Mini International Neuropsychiatric Interview for Children and Adolescents (**MINI-KID** version 7.0.2) is a short standardized diagnostic interview for DSM-5 and the International

Statistical Classification of Diseases and Related Health Problems - Tenth Revision (ICD-10) psychiatric disorders in children and adolescents. The instrument uses two to four screening questions for each disorder. If the screening questions are positively answered, additional symptom questions are given for the particular disorder. The instrument can be administered by interviewing parent(s) and adolescents together or separately. MINI-KID has an administration time of 15 to 50 minutes [52]. MINI-KID disorder classifications have shown test-retest reliability and validity comparable to other standardized diagnostic interviews. Thus, MINI-KID is a useful tool for diagnostic screening in child and adolescent psychiatry [53, 54]. Completion via video conference is allowed.

Suicidality was evaluated using the Columbia Suicide Severity Rating Scale (**C-SSRS**), a semi-structured interview validated in pediatric patients for systematic assessment of the presence and severity of suicidal ideation and suicidal behavior in clinical trials [55]. The severity scale is a 6-point ordinal scale, ranging from 1 (wish to be dead) to 5 (suicidal intent with plan). Participants who deny suicidal ideation score zero. The C-SSRS intensity scale is comprised of five items (i.e., frequency, duration, controllability, deterrents, reasons for ideation), each rated on an ordinal scale (total scores ranging from 2 to 25). These five items are completed only with participants who endorse at least one of the severity items. Those without any suicidal ideation score 0 on intensity. The behavior scale is a 5-point nominal scale that investigates interrupted, aborted, and actual suicide attempts, preparatory behavior for a suicide attempt, and non-suicidal self-injurious behavior. Telemedicine platforms such as video/phone can be utilized.

Whenever remote administrations are carried out the users should determine whether they are subject to HIPAA (US) or other health data privacy laws and use appropriate telemedicine/telecommunications tools, such as Zoom or Doximity.

